## Treatment and follow-up

Patients will be randomized 1:1 between ablation during open surgery and laparoscopic ablation

## Ablation procedure

The procedure will be performed in general anesthesia and with the patient in supine position on the operating table. The laparotomy or laparoscopy will be performed by a surgeon specialized in liver surgery. A perioperative ultrasound is performed to visualize and to guide the electrode into the tumor. Using a heat-based ablation modality which generates high temperatures, the tumor cells are destroyed leaving an ablation zone. Included center may used either radiofrequently ablation and microwave ablation as modality. However, the modality should be the same in both groups in each center.

## Endpoints and outcome measurement

### Primary outcome

- Treatment-related complications that develop within 30 days following ablation will be reported according to the Clavien-Dindo Classification, which is considered the best validated classification to rate surgical complications. The primary outcome is defined as any complication (Grade 2 or above) in the Clavien-Dindo Classification.

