## 3. Method

The study is a randomized, controlled, multicenter study in patients with liver malignancies treated at the four Danish liver surgery centers (Rigshospitalet, Odense, Århus and Aalborg). Patients with one or more liver tumor suitable for ablation as primary treatment, but not amenable for percutaneous ablation will be randomized between laparoscopic and open ablation. Opaque envelopes with patient numbers containing the randomization sequence will be opened after informed consent has been obtained. We plan to include 80 patients with 40 patients per arm. Patients will be randomized 1:1 (see below). Randomization will be stratified on center level to ensure comparable populations between the groups within each center.

Due to perioperative findings, the treatment to which the patient is randomized to may be considered not feasible or inappropriate, e.g. due to insufficient visualisation of tumor or findings that warrant a different treatment strategy. In these cases, the treatment strategy is based on the surgeons preferences. In laparoscopic cases, a minimally invasive approach should be maintained if possible, e.g. by combining laparoscopy with percutaneous ablation needle placement.

Ninety days after the procedure, the patient chart will be evaluated to register patient characteristics and outcomes. Moreover, at one month all patients will receive a CT-scan to evaluate success rate (complete ablation response). The CT-scan is part of standard of care, it is assessed by an experienced radiologist, and it is not part of this study. Before surgery and one month after, health related quality of life (HRQoL), the psychological burden and level of recovery will be assessed. Open ablation is standard of care. Thus, the intervention group will receive a treatment with assumed fewer complications and similar success rate.

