### Secondary outcomes

- Success rate of the procedure is described as rate of complete ablations one month after procedure. A complete ablation response is defined as complete absence of enhancing tissue at the tumor site after one month on CT-scan.
- Complications reported as Comprehensive Complication Index (CCI). CCI is a scoring system for overall morbidity and is reflected on a scale from 0 (no complication) to 100 (death). It is based on Clavien-Dindo classification and takes all complications after a procedure into account.
- Highest complication grade according to the Clavien-Dindo Classification
- Wound infections within 30 days is defined as wound dehiscence requiring secondary suturing or treated conservatively. Fascial dehiscence will be recorded separately.

- Postoperative liver failure is defined by the “50-50 criteria” (prothrombin time <50% and serum bilirubin >50 µmol/L on postoperative day five).
- Postoperative pain will be assessed by Visual Analogue Scale for acute and chronic pain, pre-operatively and on each post-operative day until discharge, after seven days, 14 days and one month.
- Overall and disease-free survival.
- Procedure related mortality within 90 days.
- HRQoL before and one month after the procedure will be assessed using the Danish version of The European Organization for Research and Treatment of Cancer Quality of Life (EORTC QLQ C30) and a disease specific form for patients with HCC (QLQ HCC18), cholangio carcinoma (QLQ BIL21) or colorectal liver metastases (QLQ LM21). Depression and anxiety will be assessed before and one month after procedure using PHQ-9 and GAD-7, respectively. Recovery will be assessed with the Quality of recovery (QoR-15) before and seven days after the procedure.
- Length of hospital stay defined as time in days from operation to discharge.
- Blood loss during surgery
- Need for perioperative blood transfusion
- Conversion rate in the laparoscopic group
- Duration of procedure
- Model for Endstage Liver Disease (MELD) and Child-Pugh score before operation and on postoperative day five.
- Patients experiences of undergoing ablation will be explored by individual interviews one months after the procedure.

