##### Sample size

Based on a previous study from our center, the primary outcome (any complication Grade 2 or above, Clavien-Dindo Classification) occurred in 45% of patients undergoing open ablation. The similar complication rate from another external study was 39.5%. The hypothesis is that with a laparoscopic approach, the complication rate can be reduced to 10%. With an alpha of 5% and power of 80%, we will need 60 patients (30 in each arm).

The rate of complete ablation in one month is approximately 95% for open ablations. Using a non-inferior approach and assuming a similar rate of complete ablation in the laparoscopic group, we will need 54 patients (non-inferiority limit 15%, alpha 5% and power 80%).

By including 80 patients, both above sample-size calculations will be covered, and we will have sufficient material compensate for possible excluded patients. Before randomization, we will perform training of laparoscopic ablation using a training fantom developed for the purpose. Accuracy of laparoscopic needle placement with ultrasonography will be assessed using a gel with artificial tumors and an artificial abdominal wall. In addition, we will perform 20 cases with laparoscopic ablation to ensure that technique and learning curve is sufficient compared with our standard of care (open ablation). At this point, sufficient safety and efficacy (comparable to the literature) will be

ensured prior to randomization and additional cases and additional training may be performed is necessary.

After randomization of the first 15 laparoscopic cases, we will perform an interim analysis looking only at conversion rates in the laparoscopic group due to lack of feasibility. In case of a conversion rate above 20%, sample size will be increased according to the conversion rate, e.g. 20% more patients in each group with a conversion rate of 20%. This is done to ensure sufficient power in our comparison between the open and laparoscopic technique.

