## 8. Information from patient records

Patient information will be retrieved from patient electronic charts. Patient characteristics include cancer diagnosis and stage, age, gender, primary liver disease, co-morbidities, MELD-score (patients with HCC), Child Pugh-score (patients with HCC), previous surgery, viral infections and medical comorbidities. Thirty days after the procedure, information regarding success rate of ablation, complications and lengths of stay will be collected from the electronic records. Ninety days after the procedure, procedure related mortality will be recorded. At the end of the study, complete follow-up regarding overall and disease-free survival will be recorded. The collected information will be used to assess primary and secondary outcomes and to assess whether patient characteristics are equally distributed between the two treatment groups.

The primary investigator and sub-investigators have direct access to obtain information in the patient's medical record which is necessary to carry out the research project and for control purposes, including self-control, quality control and monitoring, which they are obliged to carry out.

The information to be used in the project before consent is given from the subjects is passed on to the primary investigator.

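### The primary outcome is worded with and without a treatment-relatedness filter, the sample size uses the unfiltered form, and randomised patients who are never ablated have no start for the 30-day window

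*Combined protocol and SAP*

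**What the plan says.** The Primary outcome section contains two sentences that do not describe the same set of events. One sets a scope and a clock: "Treatment-related complications that develop within 30 days following ablation", to be reported by Clavien-Dindo grade. The other sets the endpoint: "The primary outcome is defined as any complication (Grade 2 or above) in the Clavien-Dindo Classification". The first has a relatedness condition and a start at ablation. The second has neither, and no time window.

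The Sample size section takes the unfiltered form: "the primary outcome (any complication Grade 2 or above, Clavien-Dindo Classification) occurred in 45% of patients undergoing open ablation". It then gives a second planning figure, "The similar complication rate from another external study was 39.5" per cent.

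Section 3 (Method) places randomisation after consent and before surgery. It foresees that, because of findings during the operation, "the treatment to which the patient is randomized to may be considered not feasible or inappropriate", in which case the surgeon chooses the strategy. Section 4 plans both intention-to-treat and per-protocol analyses, defines neither, and does not say which is primary.

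For deaths, Secondary outcomes lists "Procedure related mortality within 90 days", and section 8 repeats the limit: "Ninety days after the procedure, procedure related mortality will be recorded". Overall survival is a separate secondary outcome.

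**The concern.** The two sentences can be joined, with the first giving scope and window and the second the grade threshold. Relatedness is then a live condition on the primary endpoint. Alternatively the second can stand alone, in which case the filter is void and so is the 30-day limit. The text does not settle which applies.

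Three things follow if the filter is live:

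- The endpoint is narrower than the one the sample size was built on.
- Someone must decide whether each event was caused by the treatment. The plan names no criteria, no assessor and no masking for that decision. Complications come from the electronic charts. The doctoral student who includes patients at one centre also collects and analyses the data. Sections 6 and 14 state the expectation that side effects will be milder with laparoscopy.
- If the choice of reading is left until the data are in, it could be made with the results known.

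Separately, a randomised patient whose operation ends without ablation has no day from which to count 30 days. The wording gives no rule for keeping that patient in the primary comparison.

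**Working it through.** **Inputs.** Open rate 45%, laparoscopic rate 10%, alpha 5%, power 80%, 30 per arm (Sample size). 80 patients, 40 per arm (section 3). Fisher's exact test, p < 0.05 (section 4). All attribution shares below are assumptions, because the plan gives none.

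**1. The plan's own figure.** Two-sided normal approximation with pooled variance under the null, p̄ = (0.45 + 0.10)/2 = 0.275 and d = 0.35:

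n = [1.960·√(2·0.275·0.725) + 0.842·√(0.45·0.55 + 0.10·0.90)]² / 0.35² = 24.3

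Continuity correction: n′ = (n/4)·[1 + √(1 + 4/(n·d))]² = 29.8, so 30 per arm and 60 in total. The stated figure reproduces. Exact Fisher power is 83.0% at 30 per arm and 93.5% at 40 per arm.

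**2. The filter applied equally in both arms.** A share k of events is judged related, so the rates become 0.45k and 0.10k. Exact two-sided Fisher power at 40 per arm:

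| k | Open | Laparoscopic | Power |
|---|---|---|---|
| 1.0 | 45% | 10% | 93.5% |
| 0.9 | 40.5% | 9% | 89.4% |
| 0.8 | 36% | 8% | 83.7% |
| 0.7 | 31.5% | 7% | 76.0% |
| 0.6 | 27% | 6% | 66.1% |
| 0.5 | 22.5% | 5% | 53.3% |

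Power drops below the planned 80% somewhere between k = 0.8 and k = 0.7.

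**3. The filter applied unequally.** The true rate p is the same in both arms, all open events count, and a share f of laparoscopic patients' events is discounted, so p is compared with p(1 − f). The table gives the exact probability of a significant Fisher result favouring laparoscopy, 40 v 40:

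| f | p = 45% | p = 39.5% | p = 30% |
|---|---|---|---|
| 0 | 1.6% | 1.5% | 1.4% |
| 0.1 | 4.0% | 3.4% | 2.9% |
| 0.2 | 8.9% | 7.2% | 5.6% |
| 0.3 | 17.4% | 14.0% | 10.2% |

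If open events are discounted too, the excess is much smaller. At p = 45% it is 3.9% with 10% open and 20% laparoscopic discounted (40.5% v 36%), and 3.8% with 20% and 30% (36% v 31.5%).

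**4. Single-patient sensitivity, Fisher p-values.**

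- At the planned rates, 18/40 v 4/40 gives p = 0.0009. Significance is lost only when the laparoscopic count reaches 9 (five more; p = 0.058) or the open count falls to 11 (seven fewer; p = 0.083).
- Near the boundary one patient decides. 18 v 9 gives p = 0.058, and reattributing one laparoscopic event (18 v 8) gives p = 0.031. Dropping one laparoscopic patient who had an event but no ablation (18/40 v 8/39) also gives p = 0.031.

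**The case against.** The strongest reply is that the operative definition has no filter. Only the second sentence says what the primary outcome is; the first says how complications are reported. The Sample size section, the aims, the record-collection section and the Comprehensive Complication Index (which covers every complication) all run without a relatedness limit. This largely stands. It is why the point is a conflict of wording rather than a plan to filter, and it shows which way the wording should be harmonised. It does not make the relatedness phrase disappear. The sentence containing it is also the only place in the primary outcome definition that supplies the 30-day window.

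A reader might infer that the plan prescribes an unblinded causality judgement. It does not: no relatedness assessment is described at all. That it would be made by staff who know the arm is inferred from silence, and part of the protocol was not in the text reviewed.

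A reader might also take 17.4% as the expected size of the bias. It is the far end of a one-sided scenario with no discounting in the open arm. The endpoint is also one yes/no per patient, so a patient with several qualifying events changes status only if every one is discounted. Both objections stand, so the figures are given as a range.

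On patients without ablation, intention-to-treat is planned, and nothing says that patients with a changed strategy are excluded. Converted patients, and those treated by combining laparoscopy with a percutaneous needle, are still ablated. Only patients with no ablation at all are affected, and their number is not given. The missing start of the window remains for them, as does the unexplained allowance for excluded patients in the Sample size section.

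On mortality, it is tempting to read the aims, which list mortality without a limit, as contradicting the procedure-related outcome. The aims are a summary, and overall survival follow-up captures every death, so 90-day all-cause mortality is recoverable.

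**Conclusion.** The point holds as an inconsistency in the primary endpoint that should be fixed. It is not a demonstrated bias and not an error in the sample size, which reproduces at 60.

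Its size depends on how the first sentence is used. If it is ignored, only the missing window and start date matter. If it is applied evenly, the loss is power: from 93.5% to 76.0% at 70% attribution. If it is applied unevenly against a null effect, the chance of a false laparoscopic win rises from about 1.5% to between 2.9% and 17.4% over the scenarios shown, and to about 3.9% when 10% of open and 20% of laparoscopic events are discounted. The planned 45% v 10% effect would survive all but gross misattribution. The exposure lies with small or null true effects.

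These figures rest on assumed attribution shares and on taking the 45% as an unfiltered Grade 2 or above rate, as the Sample size section states. The Background cites the same 45% without a grade threshold.

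The documents do not support the stronger conclusions that the primary result is compromised as planned, or that patients without ablation will be dropped from intention-to-treat. The mortality label is a minor point.

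**What to change.** Replace the two sentences with one definition: any Clavien-Dindo Grade 2 or above complication within 30 days of the index operation, regardless of judged cause and of whether ablation was completed, in all randomised patients who had the operation. This matches the planning definition and leaves the sample size at 60, with 80 enrolled. Record relatedness as a descriptive field only.

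As a minor addition, report 90-day mortality as all-cause, with procedure-related deaths as a descriptive subset.

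The cost is one protocol sentence and one outcome label, made before outcome data are examined. The downside is that a few unrelated events add slight noise to both arms. The change removes the attribution step. It does not remove other judgement that may be unmasked, such as whether an event counts as a complication and whether it reaches Grade 2.

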### Secondary outcomes

- Success rate of the procedure is described as rate of complete ablations one month after procedure. A complete ablation response is defined as complete absence of enhancing tissue at the tumor site after one month on CT-scan.
- Complications reported as Comprehensive Complication Index (CCI). CCI is a scoring system for overall morbidity and is reflected on a scale from 0 (no complication) to 100 (death). It is based on Clavien-Dindo classification and takes all complications after a procedure into account.
- Highest complication grade according to the Clavien-Dindo Classification
- Wound infections within 30 days is defined as wound dehiscence requiring secondary suturing or treated conservatively. Fascial dehiscence will be recorded separately.

- Postoperative liver failure is defined by the “50-50 criteria” (prothrombin time <50% and serum bilirubin >50 µmol/L on postoperative day five).
- Postoperative pain will be assessed by Visual Analogue Scale for acute and chronic pain, pre-operatively and on each post-operative day until discharge, after seven days, 14 days and one month.
- Overall and disease-free survival.
- Procedure related mortality within 90 days.
- HRQoL before and one month after the procedure will be assessed using the Danish version of The European Organization for Research and Treatment of Cancer Quality of Life (EORTC QLQ C30) and a disease specific form for patients with HCC (QLQ HCC18), cholangio carcinoma (QLQ BIL21) or colorectal liver metastases (QLQ LM21). Depression and anxiety will be assessed before and one month after procedure using PHQ-9 and GAD-7, respectively. Recovery will be assessed with the Quality of recovery (QoR-15) before and seven days after the procedure.
- Length of hospital stay defined as time in days from operation to discharge.
- Blood loss during surgery
- Need for perioperative blood transfusion
- Conversion rate in the laparoscopic group
- Duration of procedure
- Model for Endstage Liver Disease (MELD) and Child-Pugh score before operation and on postoperative day five.
- Patients experiences of undergoing ablation will be explored by individual interviews one months after the procedure.

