#### 4. Statistical considerations

We will use descriptive statistics and the dataset will be described with frequencies and percentages for categorical variables and means or medians for continuous variables. Primary outcome and rates of secondary dichotomous outcomes will be compared between the groups using Fischer's exact test. Mean VAS score will be compared using Mann-Whitney U-test. To determine risk factors affecting ablation response, logistic regressions will be used in both univariable and multivariable analyses. The EORTC Quality of Life questionnaire is designed to measure cancer patients' social, physical, and psychological functions. Quality of life will be reported using the summary score with the intention of comparing patients treated with either laparoscopic or open ablation. Mann-Whitney U-test will be used to assess differences in the summary scores. Analyses will be performed both on intention-to-treat and per protocol levels. The level of statistical significance will be set to  $p < 0.05$ . All statistical analyses will be performed using R, version 4.0.3.

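### The secondary outcome named wound infection is defined as wound dehiscence, with no infection criterion, so it compares wound opening between arms rather than infection.

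*Combined protocol and SAP*

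**What the plan says.** The list under Secondary outcomes in the combined protocol and SAP contains this item: "Wound infections within 30 days is defined as wound dehiscence requiring secondary suturing or treated conservatively". The next sentence adds: "Fascial dehiscence will be recorded separately". No other section gives criteria for wound infection.

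Three other parts of the plan bear on the point:

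- **Analysis.** Section 4, Statistical considerations, says that "rates of secondary dichotomous outcomes will be compared between the groups", using Fisher's exact test. Wound infection, as a yes/no item, falls under this.
- **Other complication outcomes.** Under Primary outcome: "The primary outcome is defined as any complication (Grade 2 or above) in the Clavien-Dindo Classification", for treatment-related events within 30 days. The Comprehensive Complication Index (CCI), a secondary outcome, "takes all complications after a procedure into account". The highest Clavien-Dindo grade is also reported.
- **Data source.** Section 8: "Thirty days after the procedure, information regarding success rate of ablation, complications and lengths of stay will be collected from the electronic records". It names complications in general and gives no rule for recognising a wound infection in the chart.

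**The concern.** The outcome's name and its rule describe different events. The name is infection; the rule is separation of the wound, however managed. Nothing in the rule refers to clinical signs, discharge, culture, a recorded diagnosis or treatment for infection.

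The two arms differ in the wound itself: a laparotomy in one, small incisions in the other. The risk of a wound opening may depend on the incision apart from infection. A reported difference in wound infection could then be a difference in wound opening, and a real difference in infection could be obscured. There is also a practical problem at the four centres. An abstractor who reads a chart recording an infected but closed wound must either depart from the definition or leave the event out, and centres may resolve this differently.

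**Working it through.** The plan gives no rate, power or sample size for wound infection, so there is no figure of its own to reproduce. The two sample-size calculations rest on complications of grade 2 or above (45% v 10%) and on complete ablation (95%, margin 15%). Neither uses this outcome.

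**Step 1: apply the rule to the four possible wounds** (fascial dehiscence set aside, as the plan records it separately).

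| Wound | Infected? | Scored as wound infection? | Correct? |
|---|---|---|---|
| Superficial dehiscence, infected | yes | yes | yes |
| Closed, infected | yes | no | **no** |
| Superficial dehiscence, sterile | no | yes | **no** |
| Closed, not infected | no | no | yes |

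The rule errs in both directions. The sentence on fascial dehiscence does not cure this: it separates deep from superficial, not infected from sterile. Nor does the reference to conservative treatment, which on the natural grammar describes how a dehiscence was managed.

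**Step 2: what this does to the comparison.** Let π be the true infection rate in an arm, s the chance that an infected wound dehisces superficially, and f the chance that an uninfected wound does. Then

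recorded rate = s·π + f·(1 − π).

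- If s and f are the same in both arms, recorded difference = (s − f) × true difference. The contrast shrinks but keeps its sign as long as s > f.
- If π is the same in both arms but f differs, and s does not, recorded difference = (f_open − f_lap) × (1 − π). A difference appears although infection does not differ.

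**Step 3: illustration. Every rate here is assumed; none is in the documents.**

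- Equal s and f, true infection 15% v 5% (difference 10 points). With s = 0.5 and f = 0.02, recorded rates are 0.5 × 0.15 + 0.02 × 0.85 = 9.2% and 0.5 × 0.05 + 0.02 × 0.95 = 4.4%, a difference of 4.8 points. Over s = 0.3 to 0.7 and f = 0 to 0.05, the recorded difference runs from (0.3 − 0.05) × 10 = 2.5 to (0.7 − 0) × 10 = 7.0 points.
- No infection difference (5% in both arms), s = 0.5 in both, f = 0 laparoscopic. With f = 0.02 open, the recorded difference is 0.02 × 0.95 = 1.9 points. With f = 0.05 open, it is 0.05 × 0.95 = 4.75 points.

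The result depends entirely on s and f in each arm, and the documents supply neither. The illustration shows the mechanisms; it is not an estimate for this trial.

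**The case against.** **The sentence may only be badly worded.** It could have been meant to describe how an infected wound was managed, so that conservative treatment covers infections without resuturing. The document has other language slips. But this is the less natural grammar, and the sentence would still have to be rewritten for an abstractor to apply it that way.

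**Infections are not lost to the trial.** This stands. A treatment-related closed-wound infection of grade 2 or above counts in the primary outcome, and the CCI takes in all complications. A reader might infer that such events vanish from the results; the documents do not support that. What is lost is their identification as wound infections.

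**Little inference is at stake.** This also largely stands. Taking 10% v 2% as assumed true rates with 40 per arm, Fisher's exact test has about 11% power even with a perfect definition, and 4 v 1 events gives p = 0.36. With half the infections captured (5% v 1%), power is about 1%. The case therefore rests on whether the outcome measures what its name says, not on power.

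**A large loss of signal cannot be claimed.** A reader might infer that half or more of the infection difference would disappear. That follows only from assumed rates. With the same capture fraction in both arms and no sterile dehiscence, 4 v 0.8 events become 1.2 v 0.24 (30% captured) or 2.0 v 0.4 (50% captured). The ratio stays at 5, so this shows fewer events rather than a distorted comparison. Distortion needs dehiscence risk to differ by arm apart from infection, which is plausible here but not quantified anywhere in the documents.

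**Conclusion.** The definition does not measure the outcome it names. It misclassifies in both directions when followed as written, and no other section corrects it. The comparison reported as wound infection would be a comparison of superficial wound opening. This conclusion rests on the wording alone and needs no assumed rate.

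The size and direction of any resulting error cannot be computed from the documents. The consequence is confined to one secondary outcome: the primary outcome, both sample-size calculations and the interim look at conversions do not use it.

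Two further inferences go beyond the documents. One is that wound infection is among the clearest differences expected between the arms; the plan speaks of complications in general and of pain, and does not single out wound infection. The other is that the result could not be compared with other reports; that depends on definitions used elsewhere, which the documents do not give.

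**What to change.** Before data are abstracted:

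1. Define wound infection within 30 days by explicit infection criteria, stated so that an abstractor can apply them from the chart whether or not the wound has opened. Purulent discharge, a positive culture, or clinical signs with the wound opened or treated for infection would serve as examples.
2. Record superficial dehiscence and fascial dehiscence as two items separate from infection.

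If the sponsor prefers to keep the present rule, the minimum is to rename the outcome superficial wound dehiscence and report no wound-infection comparison from it.

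The cost is one definition and one or two extra case report form fields, completed from the same chart review. Changing it later could mean re-reading charts for infections that the current rule did not ask for.
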